1.4 Clinical Data

Botulinum toxin injection is being increasingly used “off-label” in the clinical management of chronic pain, and there have been a number of reviews highlighting the role of treating painful conditions with BTX. In their review of BTX in the treatment of chronic pain, [Rivera Dia et al. \(2014\)](#) discuss several conditions where BTX may have a role, such as trigeminal neuralgia, tension headache, chronic migraine, myofascial pain, phantom limb pain and joint pain. [Park and Park \(2017\)](#) also reviewed the experimental and clinical evidence of the mechanism by which BTX acts on various types of neuropathic pain. They described how BTX can be applied as treatment for neuropathic pain conditions such as postherpetic neuralgia, post-surgical neuralgia, diabetic neuropathy, occipital neuralgia or spinal cord injury induced neuropathic pain. They also provide clear evidence that BTX has an analgesic effect involving both peripheral and central elements of the nociceptive pathway for chronic neuropathic and nociceptive pain.

Besides use for aesthetic treatments and infocal hyperhidrosis, BTX has also been recently used experimentally in many other dermatological conditions with good results. [Campanati et al. \(2017\)](#) analysed the possible BTX “off-label” applications in dermatology and specifically collected published data on the application of BTX-A injections in keloids and hypertrophic scars. The studies reviewed revealed a great potential for BTX-A with improvement of the lesions such as lowering of the erythema, decrease of the itching, pain and tenderness sensation, but also decrease in size and flattening of the lesions. Overall, the therapeutic satisfaction of the patient and physician was good in the studies reviewed.

Of relevance for the present study, [Schwartz et al. \(2004\)](#) investigated the effects of intradermal injections of BTX-A in relieving chronic post-surgical scar pain. They showed that subjects treated with BTX-A exhibited an improved reduction in mean pain scores relative to dexamethasone (30% versus 25%) and twice the duration of effect (eight weeks for BTX-A versus four weeks for dexamethasone).

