3 INVESTIGATIONAL PLAN

3.1 Overall Study Design and Plan

The study will consist of two sequential parts, the first being to identify subjects who will potentially benefit from intradermal Dysport injection, 'responders', who will then progress to the second part, which is the double-blind study of the intradermal injection of Dysport or placebo:

- Part A: A double-blind, randomised, initial two-period cross-over run-in part, extended screening period of placebo or local anaesthetic (lidocaine),
- Part B: A single-dose, double-blind, randomised, parallel part with one of the three different doses of Dysport or placebo.

To ensure subjects will potentially benefit from intradermal injection of Dysport, they will be tested for responsiveness to local anaesthetic (lidocaine).

In Part A, and upon consent and successful screening of medical eligibility, subjects will be injected (injection test 1) during a pre-randomisation run-in period in a double blind fashion with either saline or local anaesthetic (lidocaine) and assessed for pain perception up to 24 hours post-injection. One week later, they will be crossed over, injected with the other agent (injection test 2) and assessed for pain perception up to 24 hours post-injection. Pain intensity will be scored using a 11-point NRS (from score 0 for "no pain" up to 10 for "worst possible pain").

If subjects are assessed as responders, they will enter in Part B, and will be trained and provided with an Actiwatch® to enable them to record twice a day their spontaneous NRS scores.

[figure not shown]
Before dosing on Day 1, the subjects will perform baseline assessments including a quantitative sensory testing (QST) assessing allodynia, hyperalgesia and conditioned pain modulation, completion of a QoL questionnaire, and safety assessments (physical examination, vital signs measurements, collection of adverse events (AEs) and recording of concomitant medication).

Subjects will be dosed if considered as consistent in pain perception from the screening visit (i.e. variability < 2 for the average spontaneous NRS score pre-injection tests in Part A, pre-QST and pre-dosing and as clinically plausible per investigator's judgement).

Subjects will then be assessed for pharmacodynamics and safety for a total of 16 weeks post-dose.

Subjects will be discharged from the study after safety assessments (physical examination, vital signs) during an end of study (EoS) visit.

The study design is presented in [Figure 2](#).

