3.2 Study Endpoints

3.2.1 Primary Endpoints

The primary endpoints will be:

- Time to onset, i.e. time to decrease from baseline of two points in the spontaneous NRS score,
- Peak-effect, i.e. maximal decrease from baseline in the spontaneous NRS score,
- Time to peak-effect, i.e. time to reach the peak-effect,
- Duration of effect, i.e. duration between time to onset and last timepoint for which change from baseline in the spontaneous NRS score is \geq two points.

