3.3 Study Duration

This study will consist of:

- A screening visit: 28 days maximum before IMP dosing,
- A Part A, pre-randomisation run-in period:
 - First injection test: 21 days maximum before IMP dosing,

- Second injection test: one week after first injection test, 14 days maximum before IMP dosing,
- A Part B, randomised double-blind period:
 - A baseline period including a QST and Actiwatch® training, safety assessments and a QoL: within 7 days before IMP dosing,
 - A one-day IMP dosing,
 - A 16-week randomised double-blind period.

Subjects are expected to participate in this study for a maximum of 20 weeks.

The study will be considered to have started when the first subject has provided signed informed consent and will be considered to have ended after the last subject has completed his EoS visit.

The overall study is anticipated to last approximately one year.

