Duration of effect (in days) i.e. duration between time to onset and last timepoint with decrease from baseline in the spontaneous NRS score is \geq two points Derivation: Duration is calculated as: last timepoints for which change from baseline ≤ -2 – time to onset (in days)	The mean duration of effect in each treatment group (for the subjects who reach the time to onset)

Each endpoint will be evaluated using the worst pain within the last 12 hours and using the averaged pain within the last 12 hours.

5.7.3.2 *Primary Analysis*

For each estimate, analysis will be based on the treatment policy estimand: No adjustment will be made in case of intake of rescue medication. No handling of missing data will be performed in the primary analysis.

Listings will be provided including all subjects with missing values for the 4 primary endpoints based on the NRS score. For subjects with missing values, the listings will provide all observed data related to the primary endpoints i.e. all measurements recorded prior to the missing value, any measurements recorded after the missing value, important baseline characteristics, the reason for study discontinuation and the timing of study discontinuation.

Summary table for time to onset, peak-effect, time to peak effect and duration of effect will be computed for each assessment, by treatment group and Placebo versus all Dysport groups.

The number and percentage of subjects who reach the time to onset will be presented for each assessment, by treatment group.

For each assessment, scatter plots and box whisker plots will be generated for the comparison of the peak effects between the treatment groups and all Dysport groups.

5.7.3.3 *Sensitivity Analysis*

The same analyses as described in section 5.7.3.2 will be performed on the PP population using the uncorrected parameters if important differences, i.e. at least 2 patients in the same treatment group, between the randomised population and the PP population are observed: the need for this analysis will be discussed during the blind data review meeting.

5.7.3.4 *Supplementary Analysis*

Not applicable.

5.7.3.5 *Subgroup Analysis*

No subgroup analyses will be performed.

5.7.4 *Randomised double-blind period: Analysis of Key Secondary Efficacy Endpoints*

5.7.4.1 *Endpoint, Treatment Effect and Estimand Definition*

To assess the secondary objectives, the treatment policy estimand is defined by the following key attributes:

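### The mean duration of effect counts responses still running at Week 16 or at withdrawal as finished, which pulls this primary endpoint downward by an amount the plan does not show

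*SAP*

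**What the plan says.** Protocol 3.2.1 lists this as a primary endpoint: "Duration of effect, i.e. duration between time to onset and last timepoint for which change from baseline in the spontaneous NRS score is" at least two points. SAP 5.7.3.1 derives it in days as "last timepoints for which change from baseline ≤ -2 – time to onset (in days" and names one estimate per arm: "The mean duration of effect in each treatment group (for the subjects who reach the time to onset". Protocol Table 3 names the same mean.

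Follow-up is fixed. Protocol 3.1 states: "Subjects will then be assessed for pharmacodynamics and safety for a total of 16 weeks post-dose". Spontaneous scores are collected twice a day until the end-of-study visit (Protocol 9.1.3).

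On incomplete data, SAP 5.7.3.2 states: "No handling of missing data will be performed in the primary analysis". Protocol 11.3.3.2 promised sensitivity analyses for missing data. SAP 2.6 drops them, subject to confirmation at the blind data review, for reasons that concern rescue medication. What remains is a conditional per-protocol repeat (SAP 5.7.3.3).

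SAP 5.1.2 also displays the median, quartiles, minimum and maximum of every quantitative variable. SAP 5.7.4.2 plans individual score profiles.

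**The concern.** A subject whose last available score is still at least 2 points below baseline has not been seen to lose the effect. The recorded duration is then a lower limit, fixed by the end of follow-up or by the date of withdrawal. The SAP has no rule that marks such a value, so it enters the mean like a duration whose end was observed.

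The listing of subjects with missing endpoint values (SAP 5.7.3.2) would not pick up a subject still responding at Week 16, because that duration is computed, not missing. Withdrawal adds to the problem. Protocol 4.4 replaces only withdrawals in the first six weeks, and not those for lack of efficacy. A responder with onset at Week 2 who leaves at Week 7 contributes at most 7 - 2 = 5 weeks. The analysis set is all randomised subjects, so values from replaced subjects stay in as well.

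Describing duration by dose is part of the primary objective. A reader of the report could take a lower limit for a typical duration and could not tell from the table how many responses were still running.

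**Working it through.** The plan states no expected duration, so there is no figure of its own to reproduce. The only duration in the documents is from a cited scar-pain study (Protocol 1.4): "twice the duration of effect (eight weeks for BTX-A versus four weeks for dexamethasone".

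**Inputs from the documents.** Follow-up is 16 weeks, with six subjects per arm.

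**Assumed inputs.** Onset is at Week 2, so the longest recordable duration is W = 16 - 2 = 14 weeks. The shape of the duration distribution is also assumed. Scores are taken as noise-free in steps 1 to 5.

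**1. Quantity reported.** With true duration T, the SAP's mean estimates E[min(T, W)] in place of E[T].

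**2. Exponential durations, mean m.** E[min(T, W)] = m(1 - exp(-W/m)). For m = 8: 8 × (1 - exp(-14/8)) = 8 × (1 - 0.174) = 6.6.

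**3. Other shapes.** Normal with SD 4 weeks, and lognormal with log-SD 0.6, were simulated.

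| Assumed shape | True mean (weeks) | Recorded mean | Shortfall | At the ceiling |
|---|---|---|---|---|
| Normal, SD 4 | 8.0 | 7.9 | 0.1 | 7% |
| Normal, SD 4 | 12.0 | 11.2 | 0.8 | 31% |
| Normal, SD 4 | 16.0 | 13.2 | 2.8 | 69% |
| Lognormal, median 8 | 9.6 | 8.5 | 1.1 | 18% |
| Lognormal, median 12 | 14.4 | 10.8 | 3.6 | 40% |
| Exponential | 8 | 6.6 | 1.4 | 17% |
| Exponential | 16 | 9.3 | 6.7 | 42% |

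Within each shape the shortfall grows with the true duration. Under the exponential, a true gap of 16 - 8 = 8 weeks between two arms is recorded as 9.3 - 6.6 = 2.7 weeks. Moving onset between Weeks 1 and 4 changes the exponential shortfall at a true 8 weeks from 15% to 22%.

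**4. Withdrawal.** With 20% dropout by Week 16, the exponential recorded means for true 8 and 16 weeks fall from 6.6 and 9.3 to 6.2 and 8.6, a further 0.4 and 0.7 week.

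**5. The planned median.** In the two lognormal rows fewer than half of responders are at the ceiling, and the median of the recorded values is 8.0 and 12.0, equal to the true medians. This protection needs each subject's ceiling (16 weeks minus onset) to lie above the arm's median. It does not extend to withdrawal, where a short incomplete value can fall below the median.

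**6. The opposite error.** One late score at or below -2 moves the last timepoint outward. With simulated daily scores (effect -3, onset Week 2), a true 4-week effect was recorded as 3.9 weeks at a day-to-day SD of 0.5 and as 9.3 weeks at SD 1.0. At SD 1.0 a true 14-week effect was recorded as 14.1. The true gap of 10 weeks then appears as 14.1 - 9.3 = 4.8 weeks.

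**The case against.** **The median is already planned.** This stands in part. SAP 5.1.2 displays median and quartiles, and step 5 shows that the median is often untouched by the Week 16 cut-off. But the mean remains the named estimate, the median is exposed to withdrawal, and no count of continuing responses is required.

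**The individual profiles show who is still responding.** True, and with six per arm a careful reader could find them. Nothing puts that information beside the mean.

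**At the only documented duration the bias is small.** With durations near 8 weeks it is about 0.1 to 1.4 weeks. In the lognormal case it is 1.1 weeks against a standard error of about 1.5 weeks for the mean of six. This stands as a limit on size. The sponsor does not know the duration at these doses, and the trial is meant to find out.

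**Stronger readings.** A reader might infer that the reported duration will be too short overall, most of all in the longest-lasting arm. The documents do not support that: step 6 can outweigh the shortfall in short-effect arms, and heavier withdrawal in another arm can change the order.

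A reader might also infer that the analysis hides large differences between long-lasting doses that a better analysis would recover. For assumed lognormal medians of 20 and 30 weeks, true means of 24.0 and 35.9 are indeed recorded as 12.9 and 13.7. The documents give no basis for such durations, and the remedy would not separate them. With 72% and 90% at the ceiling, the chance that at least four of six responders are there, so that the Kaplan-Meier curve never falls to one half, is 0.139 + 0.325 + 0.316 = 78% and 0.531 + 0.354 + 0.098 = 98%. That loss comes from the 16-week design.

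**Conclusion.** The point holds as a fault in how one primary endpoint is summarised. It is certain from the text that durations still running at Week 16 or at withdrawal are averaged as complete, and that this step biases the mean downward. That the bias grows with the true duration assumes similar withdrawal across arms.

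The size is not known, because it depends on the proportion still responding at Week 16. The range of about 0.1 to 1.4 weeks near the cited 8 weeks, and the larger values beyond it, rest on the assumed shapes, onset at Week 2 and noise-free scores. The sign of the total error is open because of the last-timepoint rule.

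The study has no test, power claim or decision rule, so no error rate is at risk. What is at risk is a misdescribed primary endpoint. This should be fixed before database lock but does not threaten the study.

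**What to change.** In SAP 5.7.3.1:

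- Flag a duration as right-censored when the subject's last available score still has change from baseline ≤ -2. Do this separately for worst and average pain, since the endpoint is evaluated on each.
- Report per arm, among subjects who reach onset, the number censored at Week 16 and the number censored at withdrawal.
- Give the Kaplan-Meier median and quartiles per arm, stating 'not reached' where that applies.
- If the mean is kept, label it 'mean duration observed within 16 weeks' and print the censored counts beside it.

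The cost is SAP wording, one flag per assessment and one table. No new data are needed.

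There are three limits. The median will often be not reached in a long-lasting arm of six, and no analysis can separate doses whose effects mostly outlast follow-up. The flag rests on one final score: with an effect of -3 and SD 1, a continuing responder's last score exceeds -2 with probability 1 - Φ(1) = 16%. Kaplan-Meier also assumes that withdrawal is unrelated to the remaining duration, which is why the two censored counts should be shown apart.

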		Peak-effect, i. e. maximal decrease from baseline in the spontaneous NRS score.	The mean peak in each treatment group.	
		Time to peak-effect, i.e. time to reach the peak-effect.	The mean time to reach the peak-effect in each treatment group.	
		Duration of effect, i.e. duration between time to onset and last timepoint with change from baseline in the spontaneous NRS score is ≥ 2 points.	The mean duration of effect in each treatment group (for the subjects who reach the time to onset).	

Only descriptive statistics will be provided. No statistical test will be performed.

As described in the above table, the estimand will be based on "treatment policy" strategy, which is the estimate of the treatment effect regardless of whether the subject has an intercurrent event during the study.

The following potential intercurrent events will be considered:

- The short-term use of rescue medication,
- The change in use of rescue medication.

Supplementary and sensitivity analysis will be performed to take into account these intercurrent events and to handle missing data. These analysis will be detailed in the SAP.

Analysis of the secondary endpoints

Endpoints have been defined to meet the study secondary objectives. They are presented in [Table 4](#) with their associated estimate and estimand.

Table 4 Secondary Objectives - Analysis of Secondary Endpoints

Objective	Assessments	Endpoints	Estimate of treatment effect	Estimand
To compare the efficacy of intradermal doses of Dysport to placebo.	Spontaneous pain as assessed by the spontaneous NRS score.	Change from baseline in the spontaneous NRS score to each scheduled timepoint.	Difference between each Dysport doses and the placebo group, in the mean change from baseline in the spontaneous NRS score to each scheduled timepoint.	For each estimate, the associated estimand will be based on "treatment policy" strategy (i.e. regardless of the intake of rescue medication).
	Stimulus-evoked pain as assessed by the NRS score during QST.	Change from baseline in the stimulus-evoked NRS score to each scheduled timepoint.	Difference between each Dysport doses and the placebo group, in the mean change from baseline in the stimulus-evoked NRS score to each scheduled timepoint.	For each estimate, the associated estimand will be based on "treatment policy" strategy (i.e. regardless of the intake of rescue medication).
To assess the safety and tolerability of a range of intradermal doses of Dysport	Refer to Section 11.3.1 .			

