2.3 Sample Size Determination and Power

No prospective calculations of statistical power are made.

This is an exploratory trial which will use a standard early phase dosing scheme for single escalating dose and will also generate data for future regulatory trials.

An appropriate sample size cannot be determined statistically as no previous human data from previous clinical trials are available. A sample size of six subjects per dose of Dysport has been selected. Approximately 24 subjects (3 actives and 1 placebo per group so 4x6 subjects) will be randomised in the double-blind period. Subjects who withdraw within the six first weeks from dosing will be replaced.

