2.4.2 Randomised Double-Blind Period (Part B)

Subjects will be randomised to receive Dysport 2.5 U, Dysport 2.5 U placebo, Dysport 10 U, Dysport 10 U placebo, Dysport 20 U, Dysport 20 U placebo with a ratio 3:1:3:1:3:1 (blocks of 12 subjects).

Following confirmation of eligibility after injection test 2, subjects will be assigned to a randomisation number and allocated to one of the treatment groups in a chronological order, i.e. first eligible subject will be given the first randomisation number.

Mirror lists of randomisation numbers will also be produced to allow the randomisation of replacement subjects (e.g. the subjects who withdraw within six first weeks after Investigational Medicinal Product (IMP) dosing) or to be used for the replacement of kits which could be damaged during the IMP reconstitution. For example, number CCI will be used to randomise the replacement for the subject who was randomised with number CCI.

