5.7.1.2 Statistical/analytical issues

Adjustments for Covariates

Not applicable

Handling of Dropouts or Missing Data

The strategy for missing data handling is specified in each relevant section.

Interim Analyses and Data Monitoring

Please refer to section 3.

Multicentre Studies

Not applicable

Multiple Comparisons/Multiplicity

No formal statistical significance testing will be performed.

Use of an "Efficacy Subset" of Subjects

Not applicable

Active-Control Studies Intended to Show Equivalence (if applicable)

Not applicable

Examination of Subgroups

Subgroups analyses will be detailed in the concerned sections.

5.7.2 *Pre-randomisation run-in period*

A listing presenting NRS data will be provided. The listing will present, by subject, the planned visit and timepoint, the treatment administered, the assessment dates and the NRS scores.

5.7.3 *Randomised double-blind period: Analysis of Primary Efficacy Endpoint*

5.7.3.1 *Endpoint, Treatment Effect and Estimand Definition*

To assess the primary objective, the treatment policy estimand is defined by the following key attributes:

- Population: Subjects in the randomized population
- Assessment: Worst pain and average pain within the last 12 hours as assessed by the spontaneous NRS score
- Variables (Endpoints): Described in table below
- Population-level summary (estimate of the treatment effect): Described in table below

Variables (Endpoints)	Population-level summary (estimate of the treatment effect)
Time to onset i.e. time to decrease from baseline of two points in the spontaneous NRS score. Derivation: First scheduled time point for which the change from baseline is ≤ -2 points.	The number (%) of subjects who reach the time to onset in each treatment group. The mean time to onset in each treatment group
Peak effect i.e. maximal decrease from baseline in the spontaneous NRS score. Derivation: Minimum change from baseline amongst the scheduled timepoints	The mean peak in each treatment group
Time to peak-effect i.e. time to reach the peak-effect Derivation: First timepoint for which the peak effect is reached	The mean time to reach the peak-effect in each treatment group

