For each subject, the number of incorrect perception of temperature by test will be derived for the painful and non-painful area.

Temperatures below or equal to 0°C and temperatures above or equal to 50°C are not reliable for the analyses and therefore will be excluded from the statistical analyses.

5.7.4.2 *Main Secondary Analysis*

For each estimate, analysis will be based on the treatment policy estimand: No adjustment will be made in case of intake of rescue medication.

Painful Area Mapping

Summary table for raw data and changes from baseline of the longitudinal axis and the total painful area will be provided by treatment group and measurement time and Placebo versus all Dysport groups by measurement time.

Spontaneous NRS scores

Each analysis on the spontaneous NRS score will be produced separately for the Average Numeric Pain Rating and the Worst Numeric Pain Rating.

Summary table for raw data and changes from baseline in the spontaneous NRS score will be produced by treatment group, and measurement times, only for the daily average for the average NRS scores and for the daily worst for the worst NRS scores).

The graph of arithmetic mean \pm SD over time will be provided for the change from baseline in the spontaneous NRS score (daily average for the average NRS and the daily worst for the worst NRS) with all treatment groups on the same graph. Size groups at each time point will also be presented on the graph.

The graph of arithmetic mean \pm SD over time will be provided for the change from baseline for the morning score and evening score on the same graph, separately for each treatment group.

Individual raw data and change from baseline spontaneous NRS score versus time profiles will be presented graphically for each subject with the worst numeric pain rating within the last 12 hours and the average numeric pain rating within the last 12 hours on the same graph.

Listings of individual data of the spontaneous NRS scores will be provided including all subjects with missing data. Values measured on a day where a rescue medication was taken will be flagged.

Summary table for SPID and AUE parameters will be computed for each assessment, by treatment group and visit.

For each assessment, scatter plots and box whisker plots will be generated for the comparison of SPID and AUE between the treatment groups.

Listing of individuals values of SPID and AUE will be provided.

OST analyses

Baseline assessments

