5.7.5 Randomised double-blind period: Analysis of Other Secondary Efficacy Endpoints

5.7.5.1 Endpoint, Treatment Effect and Estimand Definition

To assess the exploratory objectives, the treatment policy estimand is defined by the following key attributes:

- Population: Subjects in the randomized population
- Assessments: Described in table below
- Variables (Endpoints): Described in table below

- Intercurrent event: None
- Population-level summary (estimate of the treatment effect): Described in table below

Assessment	Variables (Endpoints)	Population-level summary (estimate of the treatment effect)
QoL assessed by the SF-36 questionnaire	Change from baseline in SF-36 scores at each scheduled timepoint	Difference between each Dysport doses and the placebo group in the SF-36 scores at each scheduled timepoint
Use of rescue medication during the study	Amount of rescue medication taken during the study	Difference between each Dysport doses and the placebo group, in amount of rescue medication intake during Part B
Use of rescue medication during the study	Time to first intake of rescue medication in days Derivation: Difference in days between date of the first intake of rescue medication and date of IMP administration.	Difference between each Dysport doses and the placebo group, in the time to first intake of rescue medication during Part B

Quality of life

QoL is assessed at day -1, week 6 and week 12 by the SF-36 questionnaire. The SF-36 consists of 36 questions divided in 9 scaled scores: General health, Reported health transition, Physical functioning, Role physical, Role emotional, Social functioning, Bodily pain, Vitality, Mental health. For more details about the derivation of the scores, see section 7. Two versions of the questionnaire were used in the study, mapping was performed to homogenize the answers, see section 7 for details about mapping rules.

In addition, a global score per patient will be derived as the sum of the individual scores at each question. It will range from 0 to 3600.

Rescue Medication

Rescue medications will be coded using the latest version of WHO-DD in effect within IPSEN at the time of database lock.

The total amount of rescue medication will be derived.

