In the following table, all dates are presented using an YYYY-MM-DD format. As an example, suppose First IMP administration = 2002-08-11 and several AEs have incomplete start dates.

Table 1 Data imputation algorithm for AE start date (AESTDT)

Description of incomplete date	Imputed numeric date	Example	
		Character date	Imputed date
Day is missing			
YYYY-MM < YYYY-MM of [First IMP admin.]	YYYY-MM-01	2002-07-XX	2002-07-01
YYYY-MM = YYYY-MM of [First IMP admin.]	Min ([First IMP admin.], AE end date)	2002-08-XX	Min (2002-08-11, AE end date)
YYYY-MM > YYYY-MM of [First IMP admin.]	YYYY-MM-01	2002-09-XX	2002-09-01
Day and month are missing			
YYYY < YYYY OF [First IMP admin.]	YYYY-01-01	2001-XX-XX	2001-01-01
YYYY = YYYY OF [First IMP admin.]	Min ([First IMP admin.], AE end date)	2002-XX-XX	Min (2002-08-11, AE end date)
YYYY > YYYY OF [First IMP admin.]	YYYY-01-01	2003-XX-XX	2003-01-01
Day, month, and year are missing			
XXXX-XX-XX	Min ([First IMP admin.], AE end date)		Min (2002-08-11, AE end date)

YYYY = non-missing year, MM = non-missing month, DD = non-missing day, XX = missing field.

In the pre-randomisation run-in period, the same algorithm as above will be followed using the first IMP administration of each period as reference date for the imputation.

If AE end date is partial, imputation could be done assuming the latest possible date (i.e. last day of month if day unknown, or 31st of December if day and month are unknown).

A4. Programming Convention for Outputs

All text fields must be left justified and numeric or numeric with some text specification (e.g.: not done, unknown, <4.5 ...) must be decimal justified.

The mean, median, lower quartile, upper quartile, SD and standard errors of the mean (SE), 95% confidence interval values will be reported to one decimal place greater than the raw data recorded in the database.

The minimum and maximum values will be reported with the same number of decimal places as the raw data recorded in the database.

In general, the maximum number of decimal places reported should be four for any summary statistic.

Percentages will be presented to one decimal place. Percentages will not be presented for zero counts. Percentage will be calculated using n as denominator. The denominator will be specified in a footnote for clarification if necessary. If sample sizes are small, the data displays will show the percentages, but in the CSR only frequencies should be described.

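### The SAP drops the protocol's dose-minus-placebo estimate for spontaneous NRS and gives no interval or baseline adjustment, so the imprecision of arms of six is not reported

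*SAP*

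**What the plan says.** Protocol 2.2 and SAP 2.1 list the comparison with placebo as a secondary objective. Protocol 11.3.3.2, Table 4, gives the estimate: "Difference between each Dysport doses and the placebo group, in the mean change from baseline in the spontaneous NRS score to each scheduled timepoint".

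SAP 5.7.4.1 says the population-level summary is in the table that follows, but that table has columns only for the assessment and the variable. SAP 5.7.4.2 then plans the output: "Summary table for raw data and changes from baseline in the spontaneous NRS score will be produced by treatment group, and measurement times". It adds mean ± SD graphs by group and individual profiles, but no difference from placebo. SAP 2.6, which lists changes from the protocol, does not record this estimate as dropped.

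In SAP 5.7.1.2 the entry under "Adjustments for Covariates" is not applicable. SAP 5.1.2 lists n, mean, SD, quartiles, minimum and maximum. The only mention of an interval is a formatting rule in Appendix A4: "SD and standard errors of the mean (SE), 95% confidence interval values will be reported to one decimal place greater". It is attached to no endpoint.

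SAP 5.1.3 defines baseline spontaneous NRS as the mean of the pre-dose scores from Day -7, so a covariate is already available.

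For SF-36, the variable in SAP 5.7.5.1 is change from baseline, but the estimate reads: "Difference between each Dysport doses and the placebo group in the SF-36 scores at each scheduled timepoint".

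**The concern.** The protocol names a between-arm contrast and the SAP supplies only its ingredients. A reader of the study report would subtract one mean of six from another and have no planned measure of how uncertain the result is. SAP 2.3 says the trial is meant to inform later regulatory trials, and for that purpose the difference and its precision are the useful results.

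Entry NRS runs from 4 to 8, and a subject who starts at 4 cannot fall as far as one who starts at 8. A chance baseline difference between two arms of six can therefore carry into the difference in change. The plan shows baseline by arm but does not allow for it in any comparison.

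**Working it through.** **Inputs from the documents**
- Arm size: "A sample size of six subjects per dose of Dysport has been selected" (SAP 2.3).
- Allocation: "with a ratio 3:1:3:1:3:1 (blocks of 12 subjects") (SAP 2.4.2).
- Power: "No prospective calculations of statistical power are made" (SAP 2.3).
- Onset threshold: 2 NRS points (Protocol 3.2.1).
- Entry NRS: 4-8 (Protocol 4.1).

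**Inputs that must be assumed.** No SD and no baseline/follow-up correlation (rho) is stated. I take SD of change 1.5 to 2.5, with 1.2 as a low case, baseline SD 1.0 to 1.5, and all six subjects per arm contributing. For scale, a uniform spread over 4-8 has SD 1.15 (continuous) or 1.41 (integers), and 2.0 is the maximum if every score lies in that range.

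**The plan's own figure.** 24/12 = 2 blocks. Two blocks give 6, 6 and 6 on Dysport and 2 + 2 + 2 = 6 on placebo, so the 4 × 6 layout reproduces. There is no power or precision figure to reproduce.

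**Interval for one dose minus placebo, unadjusted change.** Half-width = t × SD × sqrt(1/6 + 1/6). Pooling variance over four arms gives 24 - 4 = 20 df and t = 2.086.

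| SD of change | Half-width (points) |
|---|---|
| 1.2 | 2.086 × 1.2 × 0.577 = 1.45 |
| 1.5 | 1.81 |
| 2.0 | 2.41 |
| 2.5 | 3.01 |

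The half-width passes 2 points when the SD of change exceeds 2/(2.086 × 0.577) = 1.66.

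**All Dysport minus placebo (18 v 6).** 2.086 × SD × sqrt(1/18 + 1/6) = 2.086 × SD × 0.471, which is 1.5, 2.0 and 2.5 points at SD 1.5, 2.0 and 2.5.

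**Chance baseline gap.** The SE of one baseline difference is SD × sqrt(1/3), and P(gap > 1) = 2 × (1 - Φ(1/SE)). The chance for at least one of three comparisons sharing a placebo arm was simulated (400,000 trials, normal baselines).

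| Baseline SD | One comparison | At least one of three |
|---|---|---|
| 1.0 | 8% | 20% |
| 1.15 | 13% | 31% |
| 1.41 | 22% | 47% |
| 1.5 | 25% | 52% |

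**What adjustment would gain.** Write sb and sf for the baseline and follow-up SDs.
- Variance of change: sb² + sf² - 2·rho·sb·sf.
- Residual variance after adjustment: sf²(1 - rho²).
- Shift in the change difference per 1-point baseline gap: 1 - rho·sf/sb in absolute value.
- Cost of estimating the slope: a factor of about 1 + 1/18 = 1.056.

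*Equal SDs.* The variance ratio is (1 + rho)/2. At rho 0.5 this is 0.75 × 1.056 = 0.79, about 21% lower, with a shift of 0.5 point. At rho 0.3 it is 0.65 × 1.056 = 0.69, about 31% lower. At rho 0.7 it is 0.85 × 1.056 = 0.90, about 10% lower. With sb = sf = 1.2 and rho 0.5, however, the SD of change is only 1.2.

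*Unequal SDs.* Let sb = 1.2, rho = 0.5 and the SD of change be 2.0. Solving sf² - 1.2·sf + 1.44 = 4 gives sf = 2.31. The slope is 0.5 × 2.31/1.2 = 0.96, so the shift is 0.04 point. The variance ratio is 2.31² × 0.75/4 = 1.00, or about 1.05 after the lost degree of freedom, a loss of about 5%.

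**The case against.** The strongest reply is that the descriptive scope is deliberate. Protocol 11.3.3.2 and SAP 5.7.1.1 rule out tests, and the primary objective is to describe. That stands: the absence of tests and of a power calculation is not an error. It does not settle the point, because a difference with an interval is an estimate, and Table 4 itself asks for the difference.

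The reply continues that the information is already there. Baseline is summarised by group, n, mean and SD are tabulated, and group sizes and individual profiles are plotted, so a reader could see an imbalance and compute an unadjusted interval. This is largely right and limits the size of the point. It still leaves a protocol-defined estimate to be worked out by hand. If a population-level column was lost from the table in SAP 5.7.4.1 when the text was read, SAP 5.7.4.2 would still plan no output for it.

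A reader might infer three stronger claims that the documents do not support:
- *The arms are not comparable, or the difference is biased.* Arms are randomised, so the change-score difference is unbiased over randomisation.
- *A baseline gap above 1 point is likely.* For a given placebo comparison it is 8-25% at SD 1.0-1.5, and 39% even at SD 2.0.
- *Adjustment brings a fixed gain, such as 25% less variance.* That needs equal SDs at baseline and follow-up with rho 0.5. With baseline SD 1.2 and rho 0.5, it cannot hold together with an SD of change of 2.0.

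Nor is the interval format in Appendix A4 a sign of an intended interval. The same appendix formats p-values, and no tests are planned.

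**Conclusion.** The point holds as a gap between the protocol and the SAP, and as a cheap improvement in reporting. The SAP does not deliver the Table 4 estimate for spontaneous NRS and attaches no interval to it.

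The imprecision is material if the SD of change is about 1.7 or more, because the interval for one dose minus placebo then spans at least ±2 points. At SD 1.2 it does not, so it should not be said without qualification that a 2-point difference lies within chance. The baseline-gap figures rest on an assumed SD. They could be higher, because the Day -7 to Day 1 baseline can fall outside 4-8 and the entry criterion does not say whether it means average or worst pain. They could also be lower, because the baseline averages up to a week of scores.

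Adjustment for baseline is reasonable, since the covariate is already collected, but its effect runs from a variance reduction of 20% or more to a loss of about 5%.

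For SF-36, a reader might infer that baseline is ignored. SAP 5.7.5.2 tabulates change from baseline by group, so only the wording of the estimate needs correction.

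**What to change.** - **SAP 5.7.4.1:** add the population-level summary from Protocol Table 4.
- **SAP 5.7.4.2:** report each Dysport dose minus placebo, and all Dysport minus placebo, in change from baseline in spontaneous NRS at Weeks 6, 12 and 16, each with a 95% CI. Take them from one four-arm model with baseline NRS as covariate, separately for average and worst pain as the section already does. Label the result as descriptive estimation without tests, and keep the existing tables and graphs.
- **SAP 5.7.1.2:** replace the not-applicable entry with baseline NRS for this estimate, and record the addition in SAP 2.6.
- **SAP 5.7.5.1:** word the SF-36 estimate as a difference in change from baseline, to match the endpoint and the tables in 5.7.5.2.

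No new data are needed. The cost is SAP wording, a small model for each pain score and timepoint, one degree of freedom (19 instead of 20), and an assumption of a common baseline slope across arms. If the sponsor prefers not to adjust, the unadjusted difference with its 95% CI would still restore the protocol's estimate and show its precision.
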